## Supplemental Analyses

CCI

CCI

## Background Information on Outcomes

### HAQ and mHAQ:

The Health Assessment Questionnaire Score is calculated as a total score divided by the number of non-missing measures. The score is a composite measure across 20 questions of the following 8 realms: dressing & grooming, arising, eating, walking, hygiene, reach, grip and activities. Please see the subject questionnaire for details on the questions asked.

From the online documentation, twenty specific activities are assessed on a 4-point Likert scale where 0 = without difficulty, 1 = with some difficulty, 2 = with much difficulty, and 3 = unable to do. The 20 activities are grouped into 8 functional categories with each category given a single score equal to the maximum value of their component activities (0, 1, 2, or 3). Total score is between 0-3.0 in 0.125 increments with increasing scores indicating worse functioning with 0 indicating no functional impairment and 3 indicating complete impairment.

The modified HAQ considers 8 specific questions that are representative of the realms listed above. The questions considered are “dress yourself, including tying shoelaces and doing buttons”, “get in and out of bed”, “lift a full cup or glass to your mouth”, “walk outdoors on flat ground”, “wash and dry your body”, “bed down to pick up clothing from the floor”, “turn faucets on and off”, and “get in and out of a car”. The scale is considered missing if the number of non-missing components is 6 or less.

From the online documentation, eight activities are rated on a 4-point Likert scale where 0 = without any difficulty, 1 = with some difficulty, 2 = with much difficulty, and 3 = unable to do. The mHAQ scale ranges from 0-3 with higher scores indicating worse functioning.

The following references give details on the coding of the HAQ.

Redelmeier et al. Arch Int Med 1993;153:1337-42

Wells et al J. Rheumatol 1993;20:557-60

Guzman et al. Arth Rheum 1996 39:5208

The following references give details on the coding of the mHAQ.

[https://www.niehs.nih.gov/research/resources/assets/docs/haq\\_instructions.pdf](https://www.niehs.nih.gov/research/resources/assets/docs/haq_instructions.pdf)

(Uhlir, et al, Rheumatology, 2006)

This reference states that “A change in MHAQ of 0.25 has been suggested as clinically meaningful” and references the Wolfe et al article.

<http://onlinelibrary.wiley.com/doi/10.1002/acr.20620/full>

### DAS28 and mDAS28:

DAS28 is an indicator of disease activity that is calculated using a weighted combination of four measures: tender joint counts (0-28), swollen joint counts (0-28), erythrocyte sedimentation rate (ESR) and patient reported global health assessment (0-100). The DAS28 range was 0 to 9.4. Laboratory values were not required in the Corona registry, so this information is missing for many of our patients. Therefore, we suggest that a modified DAS28 measure be used instead. This measure is also a weighted combination of measures: tender joint counts (0-28), swollen joint counts (0-28), modified health

assessment questionnaire (mHAQ) measure (0-3), patient reported pain (0-100), physician reported global health assessment (0-100) and patient reported global health assessment (0-100). As [name] mentioned, we have published a manuscript validating the mDAS for use in place of the DAS measure (Bentley, Greenberg and Reed, The Journal of Rheumatology, 2010).

The mDAS28 ranges from 0-9.4 and higher scores indicate higher disease activity.

ACR20/50/70 and mACR20/50/70:

ACR20 is defined as a composite endpoint; if a patient has a response, then he/she shows at least a:

- 20% improvement in tender joint count and
- 20% improvement in swollen joint count and
- At least a 20% improvement in 3 out of 5 of the following endpoints:
  - Patient pain assessment (0-100)
  - Patient global assessment (0-100)
  - Physician global assessment (0-100)
  - Patient self-addressed disability (0-3) - mHAQ
  - Acute phase reactant (erythrocyte sedimentation rate - ESR or C reactive protein - CRP)

ACR50 and ACR70 are defined in a similar fashion.

Because the measures include laboratory values that were not collected for all patients as part of routine clinical practice, e.g. ESR and CRP, a modified ACR20/50/70 is suggested. The mACR20 is also defined as a composite endpoint; if a patient has a response, then he/she shows at least a:

- 20% improvement in tender joint count and
- 20% improvement in swollen joint count and
- At least a 20% improvement in 2 out of 4 of the following endpoints:
  - Patient pain assessment (0-100)
  - Patient global assessment (0-100)
  - Physician global assessment (0-100)
  - Patient self-addressed disability (0-3) - mHAQ

mACR50 and mACR70 are defined in a similar fashion.

The Ranganath et al article (ACR remission criteria and response criteria, Clinical and Experimental Rheumatology, 2006) provides justification for the ACR measure.

Patient pain

The question asked is: "How much pain have you had because of your arthritis IN THE PAST WEEK?". The scale ranges from 0-100 with 0 being no pain and 100 being pain as bad as it could be.

Patient fatigue

The question asked is: "How much of a problem has unusual fatigue of tiredness been for you IN THE PAST WEEK?" The scale ranges from 0-100 with 0 being fatigue is no problem to 100 fatigue is a major problem.

### EQ-5D Index

The EQ-5D descriptive system comprises the following 5 dimensions: mobility (1-3), self-care (1-3), usual activities (1-3), pain/discomfort (1-3) and anxiety/depression (1-3). Each dimension has 3 levels: no problems (1), some problems (2), severe problems (3). The respondent is asked to indicate his/her health state by ticking (or placing a cross) in the box against the most appropriate statement in each of the 5 dimensions.

The EQ-5D index provides an overall measure ranging from 0 to 1 where 0 is death and 1 is perfect health. The scoring algorithm was derived from: Shaw JW, Johnson JA, Coons SJ.

U.S. Valuation of the EQ-5D Health States: Development and Testing of the D1 Valuation Model. Medical Care. Submitted 2004.

## Statistical Analysis Plan (SAP) - Pfizer 054c

### Title: QD Efficacy Analysis – Addendum

As a complement to the primary analysis, an exploratory analysis will be conducted using the full pre- matched analysis population (N = 450). In addition to the results, we will provide a summary describing new analyses, methods used including differences from prior methods, and interpretation of results.

**Objective 1:** Repeat the primary analyses (Tables 1 – 3\_adj) using the full analysis population (N = 450).

New analyses will be incorporated into the existing report and tables will be named so as to avoid confusion with pre-existing analyses. Along with each newly analyzed section, we will describe any changes from the previous analyses and we will provide interpretation of all results.

Analysis: We will update the analyses in the following ways:

Table 1: Will not be altered. This table shows baseline characteristics of the full analysis population.

Table 1a: Will not be re-generated. Table 1a showed baseline characteristics among the PS matched population and will be excluded from this analysis.

Table 2: Will be generated using the full analysis population.

Table 2\_adj: Will be generated using the full analysis population. The unadjusted estimate will remain unadjusted, and the adjusted estimate will be generated using a model which considers imbalanced covariates (as defined by the standardized differences from Table 1). We will perform model selection to ensure that we optimize the combination of a high level of explanatory power and a concise number of degrees of freedom.

Table 2a: Will be generated using the full analysis population. Table 2b: Will be generated using the full analysis population. Table 3: Will be generated using the full analysis population.

Table 3\_adj: Will be generated using the full analysis population. Adjusted estimates will be calculated similar to those in Table 2\_adj.

**Objective 2:** Provide detailed information on exclusion criteria used when selecting the 297 eligible QD initiators (out of the original 611 initiators) as well as the 153 BID initiators (out of the original 258 initiators).

Analysis: We will update the sample selection figure to reflect the sample derived from the end of September 2018 version of the registry. Reasons for exclusion will be detailed and will include: initiated treatment too late (i.e. after 3/31/2018) and so had not reached time for 6 month visit, no 6 month visit despite having initiated treatment

longer than 6 months ago, no valid CDAI at initiation, and no valid CDAI at 6 months despite attending visit.

	5 mg BID (N/%)	11 mg QD (N/%)
Initiated after 3/31/2018 (not reached 6 months)		
No 6 month visit		
No valid CDAI at initiation		
No valid CDAI at attended 6 month visit		

In addition to the analyses, we will provide an interpretation of the results, including thoughts on the reasons for the listed difference. We will also assess the potential biases that may be introduced into the analyses due to the exclusion criteria.

**Objective 3:** Repeat the primary analyses (Tables 1 – 3\_adj) using a propensity score trimmed population.

To ensure the adjusted analyses do not extrapolate due to the use of dissimilar patients, the propensity score which was previously used to match patients can be used to trim the population of the initiations for which there is no similar initiation in the other group – carrying out the multivariable adjustment for patients on “common support” across the covariates of interest. The propensity score distribution will be examined in both populations and each population will be trimmed for extreme values: patients in one group with propensity scores higher or lower than scores in the other group will be “trimmed” (i.e., excluded from analyses). Only patients with scores overlapping both distributions will be included in the analysis.

Analyses: The analyses will be updated in the same way as in objective 1, using the propensity score trimmed population instead of the full analysis population. When considering covariates to include in adjusted analyses, we will adjust for age, gender, duration of RA, and baseline CDAI (as in the primary analyses), in addition to any imbalanced covariates (those with standardized difference > 0.2). New analyses will be incorporated into the existing report and tables will be named so as to avoid confusion with pre-existing analyses. We will update Table 2 to include the results of a chisquare test in addition to the original t-test results and we will provide an interpretation of both. Along with each newly analyzed section, we will describe any changes from the previous analyses and we will provide interpretation of all results.

CCI  
[Redacted]

[Redacted]

CCI [Redacted]

[Redacted]

[Redacted]

CCI [Redacted]

[Redacted]

CCI [Redacted]

[Redacted]

CCI [Redacted]

CCI

[Redacted]

CCI

[Redacted]

[Redacted]

[Redacted]

[Redacted]

[Redacted]

CCI

[Redacted]

[Redacted]

CI

CCI

CCI

**Proposed Analyses:**

1. Repeat all analyses (Tables 1 – NI) using more recent data

Of the previously defined cohort of 869 tofacitinib initiators (611 initiators of 11 mg QD, and 258 initiators of 5 mg BID) who initiated on or after 2016/02/01, 306 patients (245 initiators of 11 mg QD, and 61 initiators of 5 mg BID) had no available follow-up visits post-initiation using the original 2018/09/30 version of the RA registry, and so were excluded from analysis. In order to remedy the high proportion of initiators with no follow-up, we will consult the most recent data available (RA registry version 2019/08/31) in order to provide the most complete understanding of the availability of follow-up for these patients.

Preliminary investigations indicate that 117 of these 306 initiators have an eligible six-month follow-up visit available and can be included in further analyses (Appendix Table). With the addition of these patients, we would proceed to further analyses with 401 (66%) out of the 611 initiators of 11 mg QD, and 172 (67%) out of the 258 initiators of 5 mg BID (Table 2). After updating the eligible sample and replicating all analyses, the report previously delivered on CCI [REDACTED] will be re-created. (Note: final analyses will also require valid CDAL measurements at initiation and six-month follow-up, which will exclude a small number of patients from these cohorts)

Table 2. Tofacitinib initiators' eligibility status categories by initiation dose, using 2019/08/31 version of RA database

	All Initiators	11 mg QD	5 mg BID
After 1/31/2016	869	611	258
No follow-up	113 (13%)	79 (13%)	34 (13%)
First follow-up not during first year	67 (8%)	51 (8%)	16 (6%)
Follow-up within first year BUT no six-month visit	116 (13%)	80 (13%)	36 (14%)
Eligible six-month visit	573 (66%)	401 (66%)	172 (67%)

2. Perform sensitivity analysis of primary outcome

Using the updated eligible cohort detailed in Table 2 above, 34% of initiators will remain ineligible for analysis. We will present an additional table similar to Addendum Full Table 2 CCI which will include all 869 initiators of 11 mg QD and 5 mg BID, treating those who are not eligible due to lack of six-month follow-up visit as not achieving MCID in CDAI.

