### Population for Overall Aim:

For the primary analysis comparing QD to BID patients, we will consider those patients who initiated tofa 5 mg BID on or after February 2016 and those that initiated tofa 11 mg QD after it became available in February 2016. Although the sample size will be smaller than if we consider all tofa 5 mg BID patients, the addition of those patients may introduce noise since there is the possibility that they could differ from the more recent initiators. Therefore, we will consider the cleaner cohort of all patients initiating tofa on or after February 2016.

In order to adequately measure the outcome, the initiators will also be required to have a follow-up visit at 6 months (+/- 3 months) after tofacitinib initiation.

The data cut to be used will be the most recent available.

With regards to dosing, patients can be categorized as follows:

QD dosing: once-daily tofacitinib 11mg

BID dosing: 5mg twice-daily

Other: other dosages including 10 mg and will also include not specified

Those in the "other" category will not be considered in these analyses.

The first initial look at the data has indicated that the tofa 5 mg BID group differs on some characteristics from the tofa 11 mg QD group. To account for these differences, in a second look at the data, we propose to consider models adjusted for no more than 10 covariates. This will provide a robust analysis, while preserving sample size. The full propensity score analysis will be done in the final look at the data when the sample size is large enough (as per preliminary power calculations on page 23).

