In this second look with adjusted models, we propose to consider covariates with standardized differences > 0.2 as well as age, gender, CDAI and duration of RA (e.g. gender, age, duration of RA, current statin use, prior cDMARD use, prior non-TNF use, current concomitant therapy, CDAI and EQ-5D) in adjusted models. When considering change in outcome, we will also include the baseline level of that covariate in the model (e.g. for change in CDAI, consider baseline CDAI). For the continuous outcomes, mean differences within subject adjusted for covariates will be assessed using linear regression models (least squares means and 95% CIs). For binary outcomes, we will consider multivariable logistic regression models (ORs and 95% CIs). For the primary outcome, the adjusted OR (95% CI) will give the odds of having MCID improvement in the 11 mg QD initiator group as compared to the odds in the 5 mg BID initiator group after adjusting for covariates; the 5 mg BID initiator group will be the reference group. The interpretation will be similar for the other binary secondary outcomes. Please refer to **Table 2\_adj** for the primary outcome and **Table 3\_adj** for the secondary outcomes.

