**Table 2a: Other outcomes of 11 mg QD vs. 5 mg BID Initiators**

*Table generated “after propensity score matching” only for the final analysis.*

	11 mg QD Initiators N=	5 mg BID Initiators N=	p-value*
Other outcomes	Response Rate	Response Rate	
Switching status**			
% Remained on drug at 6 month visit			
% Discontinued initiated drug and did not start another biologic at/before 6 month visit			
% Switched initiated drug to another biologic at/before 6 month visit			

\*P-value will be from a 2 degree of freedom chi-squared test investigating the relationship between the two treatment arms and the 3 switching status categories.

\*\*The “discontinued initiated drug” category will be defined as discontinuation of tofacitinib without a new biologic started. The “switched initiated drug” category was defined as discontinuation of tofacitinib with a new biologic started.

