**Justification for proposed analyses:**

The original analysis excluded 48% of initiators (51% of 11 mg QD initiators and 40% of 5 mg BID initiators) due to lack of eligible follow-up. When incorporating the most updated follow-up information, the exclusion rate will be reduced to 33%. In addition to the raw reduction in exclusion rate, the rates will be balanced between initiation dose groups (34% of 11 mg QD initiators excluded compared to 33% of 5 mg BID initiators excluded).

Additionally, presenting the rate of achievement of MCID in CDAI while assuming that all ineligible initiators do not achieve MCID will attempt to determine the potential effects of a theoretical worst-case scenario.

CCI

[Redacted]

CCI

[Redacted]

Where currently we only consider visits between 3 and 9 months as eligible to be the six-month follow-up visit, we will widen the window of time defining a six-month follow-up visit, considering any visit within the first year after initiation as eligible to be the six-month follow-up visit. This altered definition will create a larger analysis cohort (Table 3); therefore, we will replicate all analyses performed CCI [Redacted] using this new sample of 689 patients.

CCI

[Redacted]

CCI

[Redacted]

[Redacted]

CCI

[Redacted]

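### In the readable text, the 869-patient sensitivity analysis and the full- and trimmed-population Table 2a are crude comparisons with no adjusted counterpart, although the SAP reports baseline differences between the groups

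*SAP*

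**What the plan says.** **The crude tables.** In the SAP shells, Table 2 gives response rates for the primary outcome with a two-group t test. For Table 2a (remained, discontinued or switched) the "P-value will be from a 2 degree of freedom chi-squared test". Neither test uses covariates. Both shells are marked for use after propensity score matching, so comparability was to come from the sample.

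**Their reuse.** The QD Efficacy Analysis Addendum, Objective 1, moves these tables to the pre-matched population of 450: "Table 2: Will be generated using the full analysis population", and the same for Table 2a. Objective 3 repeats this in a propensity-score-trimmed population. Adjusted estimates are described only for Table 2_adj (primary outcome) and Table 3_adj (secondary outcomes). Neither of those shells contains switching status.

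**The 869-patient table.** In the later addendum (Proposed Analyses, item 2) the SAP says: "We will present an additional table similar to Addendum Full Table 2". It covers all "611 initiators of 11 mg QD, and 258 initiators of 5 mg BID", and those without a six-month visit count as not achieving MCID. The justification describes the output as "presenting the rate of achievement of MCID in CDAI while assuming that all ineligible initiators do not achieve MCID". The readable text names no model and no covariates.

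**What the SAP says about comparability.** Analysis for Overall Aim makes similarity of the groups a condition for comparing outcomes. Population for Overall Aim reports from the first look that "the tofa 5 mg BID group differs on some characteristics from the tofa 11 mg QD group". Its example adjustment set is gender, age and duration of RA, followed by "current statin use, prior cDMARD use, prior non-TNF use, current concomitant therapy, CDAI and EQ-5D". Objective 3 still adjusts after trimming, including for covariates with a standardized difference above 0.2.

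**The concern.** Table 2 was made for a sample in which matching had already dealt with measured imbalance. Used on unmatched patients, the same crude table loses that protection. In Objectives 1 and 3 the primary outcome gets it back through Table 2_adj. The 869-patient analysis and Table 2a do not.

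The 869-patient table is the only readable analysis of the primary outcome that keeps every initiator. It exists to show whether the answer survives a worst-case view of the missing visits. The main result is matched or adjusted, so moving from it to a crude table changes two things at once: the handling of missing visits and the control of baseline differences. A shift might be blamed on the exclusions when imbalance produced it, or imbalance might mask a real effect of the exclusions. The crude Table 2a comparison of stopping and switching is open to the same bias.

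**Working it through.** **1. The plan's own counts.** Proposed Analyses gives "401 (66%) out of the 611 initiators of 11 mg QD, and 172 (67%) out of the 258 initiators" of 5 mg BID as having an eligible visit.
- QD: 79 + 51 + 80 + 401 = 611; 401/611 = 65.6%.
- BID: 34 + 16 + 36 + 172 = 258; 172/258 = 66.7%.
- Overall: 573/869 = 65.9% eligible, so 34.1% are excluded. (The justification gives 33% overall; the counts agree with the 34% in item 2.)

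**2. Does differential follow-up matter by itself?** Assume 50% response among eligible patients in both groups, the SAP's planning value. Counting the rest as non-responders gives 0.5 × 0.656 = 32.8% for QD and 0.5 × 0.667 = 33.3% for BID, a difference of −0.5 points. Unequal follow-up adds little. What remains is baseline imbalance.

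**3. Which comparisons have an adjusted version in the readable text?**

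| Comparison | Crude table | Adjusted counterpart |
|---|---|---|
| Primary outcome, full population (450) | Table 2 | Table 2_adj |
| Primary outcome, trimmed population | Table 2 | Table 2_adj |
| Secondary outcomes, full and trimmed | Table 3 | Table 3_adj |
| Stopping/switching, full and trimmed | Table 2a | none |
| Primary outcome, all 869 | similar to Full Table 2 | none |

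**4. Precision of the 869-patient difference.** With about 33% response overall, the 95% half-width is 1.96 × √[0.33 × 0.67 × (1/611 + 1/258)] = 0.068, or 6.8 points. At 50% response it would be 1.96 × √(0.25/611 + 0.25/258) = 0.073, but that is not the rate in this table.

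**5. Illustrative bias (assumptions, not document figures).** The example covariate list has nine entries. Age, gender, CDAI and duration are always included, which leaves five to enter under the > 0.2 rule. Assume each has a standardized difference of 0.2 to 0.3, each SD is worth 2 to 4 points of response, and all act in one direction.
- Among patients with an outcome: 5 × 0.2 × 2 = 2 points, up to 5 × 0.3 × 4 = 6 points.
- In the 869, about 34% have a fixed outcome, so the shift shrinks by 573/869 = 0.66 if the factors do not also predict follow-up: 2 × 0.66 = 1.3 points, up to 6 × 0.66 = 4.0 points.
- Relative to sampling error, the upper end is 4.0/6.8 = 0.58 of the half-width.

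**6. A second set of assumptions.** Take no formulation effect and three binary factors at standardized difference 0.2, all in one direction, each shifting response by 10, 20 or 30 points. The difference among eligible patients is then 3, 6 or 9 points. Centring response on 50%, the 869-patient difference is:
- 0.515 × 0.656 − 0.485 × 0.667 = 1.5 points;
- 0.530 × 0.656 − 0.470 × 0.667 = 3.4 points;
- 0.545 × 0.656 − 0.455 × 0.667 = 5.4 points.

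A nominal 5% test would reject about 7%, 16% or 33% of the time. One such factor alone gives 5% to 7%.

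**7. Does trimming remove the need to adjust?** A simulation with 297 vs 153 patients, one continuous confounder and no formulation effect says not. Trimming to the overlapping range kept about 98% of patients and lowered the standardized difference only from 0.20 to 0.18, or from 0.40 to 0.36. For a generic binary outcome, the unadjusted test after trimming rejected 7–9% of the time (0.20) or 13–24% (0.40). The covariate-adjusted test stayed at 4–5%.

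**The case against.** **There is a like-for-like comparator.** Item 1 of the same Proposed Analyses repeats all analyses in the updated eligible cohort, so the crude table in eligible patients can be set beside the crude table in all 869. A later item also compares eligible and non-eligible initiators at baseline. This stands: a reader might infer that the effect of exclusions cannot be separated from imbalance at all, and that goes too far. But comparing two crude tables shows only how a crude estimate moves. It does not show whether the adjusted conclusion survives the worst-case handling of missing visits.

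**Redaction.** A redacted block follows the table name in item 2, and nearby text is also withheld. An adjusted version may be described there. The point is therefore limited to the readable text. The p-value in the 869-patient table is likewise inferred from the Table 2 shell.

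**Purpose.** The 869-patient table is a bounding display with no decision rule in the readable text. Objective 1 is expressly exploratory, Table 2a is listed under other outcomes, and it is already planned in the matched analysis. This lowers the severity. It does not explain why the SAP's own condition of comparable groups should lapse here.

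**Imbalance is not yet confounding.** A reader might infer that these p-values carry known confounding. The documents do not support that. They report differences at the first look, give no imbalance for the 869 or the trimmed set, and link none of the factors to response. The covariate list is only an example.

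**Conclusion.** The gap is real in the readable text and modest in weight. Two sets of comparisons, the 869-patient primary-outcome table and Table 2a in the full and trimmed populations, are specified without adjustment in groups that the SAP reports as different at baseline. Imbalance may bias them.

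The direction and size cannot be determined from the documents. Under the five-factor assumptions the 869-patient shift is about 1.3 to 4 points, against a half-width of about 6.8. A reader might infer that the bias rivals sampling error, but under those assumptions it reaches at most about 0.6 of the half-width, and only if all five factors act in one direction. Opposing directions would make it smaller; stronger links to outcome would make it larger, as the 5.4-point case shows.

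The point does not extend to the primary outcome in the full and trimmed populations, which keeps Table 2_adj, or to the matched final analysis. It is worth correcting because the remedy is cheap and the 869-patient table is the only readable primary-outcome analysis that retains all initiators.

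**What to change.** - **869-patient analysis.** Keep the crude rates. Beside them report a logistic model of the Table 2_adj type, with age, gender, duration of RA and baseline CDAI plus any covariate with a standardized difference above 0.2, as in Population for Overall Aim and Objective 3. Base the interpretation on the adjusted estimate. If the redacted text already provides this, say so in the readable text.
- **Missing data rule.** State in advance how missing baseline covariates are handled, for example by a missing category or imputation. Baseline CDAI needs its own rule: the addendum lists initiators without a valid value, and a complete-case model would drop patients from an analysis meant to keep everyone.
- **Table 2a in Objectives 1 and 3.** Label the crude p-value descriptive, or drop it. A multinomial model with the same covariates is optional.

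The cost is one extra regression on covariates already planned for Table 1, and one step for missing covariates. No new data are needed.
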